### 11.3. Description of Statistical Methods

#### 11.3.1. Analysis Populations

- Intent-to-treat (ITT) Analysis Set: The ITT analysis set will consist of all randomized subjects.

---

- Modified Intent-to-treat (mITT) Analysis Set: The mITT analysis set will consist of randomized subjects who receive at least 1 dose of investigational product (IP) regardless of any protocol deviation. The treatment arm will be the arm to which they were randomized, regardless of what treatment they received.
- Safety Analysis Set: The safety analysis set will consist of randomized subjects and who receive at least 1 dose of IP. Subjects will be analysed according to treatment received. This population will be used for baseline characteristics and for safety data summaries
- Per-protocol (PP) Analysis Set: The PP analysis set will consist of all mITT subjects who do not have major protocol deviations that may affect the primary efficacy endpoint. These deviations will be determined before the study database will be closed.
- The PK Population will consist of all subjects who received study drug and provided evaluable PK data.

Subjects who prematurely discontinue from the study will be included in the safety population but may be excluded from the PK analysis population unless sufficient data is provided for PK evaluation. Subjects who are included in the PK population but have missing data for a particular endpoint will not be included in the analysis for that endpoint. Unused data, measurements from excluded subjects, unscheduled collections, or extra measurements, will not be included in the summaries, but will be presented in the subject listings.

The primary analysis will be performed on the modified intent-to-treat population (mITTs), i.e. all randomized patients who had at least one treatment intake. The analysis of the primary endpoint will be also assessed with the PP and ITT populations as per sensitivity analysis.

### **11.3.2. Demographics, baseline characteristics**

Demographics and medical history will be collected during Screening and summary of data will include date subject signed the informed consent. The subjects' age, height, weight, and baseline characteristics will be summarized by treatment using descriptive statistics, while gender, race and other categorical variables will be provided using frequency tabulations. Medical history data will be listed. Medical history data will include any prior reaction to drugs, use of alcohol and tobacco, history and treatment (if any) of cardiovascular, pulmonary, gastrointestinal, hepatic, renal, immunologic, neurologic, or psychiatric diseases, and confirmation of relevant inclusion criteria.

### **11.3.3. Subject Disposition**

Subject disposition (analysis population allocation, entered, discontinued, along with primary reason for discontinuation) will be summarized using frequency and percent for

---

both treatment and follow-up phase. A summary of subjects screened and enrolled will be provided.

A subject is considered to complete the study if he/she completed the 72 week period OR if she/he completed at least 48 week at study completion (i.e. after the last subjects have completed the study up to at least 48 week). Withdrawal from treatment or protocol deviations will not necessarily preclude from recording the respective follow-up information. Efforts will be made to follow all subjects up to 72 or 48 weeks after start of treatment (or to study end if that occurs earlier) and collect data as planned.

#### **11.3.4. Efficacy Analysis**

##### **11.3.4.1. Hierarchical multiple testing**

A hierarchical multiple testing procedure will be used to evaluate superiority of the primary endpoint, followed by the evaluation of superiority of the key secondary endpoints. A fixed sequence stepwise multiple testing procedure at the 0.05 level will be performed in the following pre-specified hierarchical order:

- I. Primary endpoint: change from baseline ALSFRS-R score after 48 weeks.
- II. Key secondary endpoint: CAFS at 48 weeks
- III. Key secondary endpoint: Survival time (death, tracheostomy or initiation of non-invasive ventilation for more than 20 hours a day for more than 10 consecutive days) over 72 weeks

Each step will be considered confirmatory if all previous steps were successful (i.e. if superiority was achieved). If any of the previous steps were unsuccessful, the subsequent steps are regarded as exploratory.

##### **11.3.4.2. Primary Efficacy Endpoint**

The primary endpoint is defined as the change from baseline in ALSFRS-R score after 48 weeks (primary time point).

For the primary analyses placebo (reference) multiple imputation will be applied to impute missing data for any subjects (i.e. from both treatment arms) who discontinue treatment early, irrespective the reason for drop-out, and for which no data was collected after treatment discontinuation. A total of 20 imputed data sets will be created.

Linear mixed modelling for repeated measures will be applied on each of the imputed data set to estimate the average (lsmeans) treatment effects and the treatment difference (estimand) of the change from baseline of ALSFRS-S score at week 48.

The model will include factors for treatment, time, treatment-by-time interaction, and concomitant use of riluzole (yes/no) as fixed effects and baseline ALSFRS-R score and slope of disease progression (based on change in ALSFRS-R score) as (random) covariates.

The results of the 20 imputed data sets will be combined to obtain the final estimate of the treatment difference with 95% confidence interval and p-value.

The primary analysis will be performed on the modified intent-to-treat population (mITTs), i.e. all randomized patients who had at least one treatment intake

#### 11.3.4.3. Secondary Efficacy Endpoints

##### Key secondary endpoints

- Combined assessment of function and survival (CAFS) at 48 and 72 weeks
- Survival time, i.e. time to death, tracheostomy or initiation of non-invasive ventilation for more than 20 hours a day for more than 10 consecutive days, over 72 weeks

The CAFS will be used as key secondary endpoint as it combines information on survival and ALSFRS-R scores. For this endpoint, each patient's outcome will be ranked: the worst patient outcomes will receive the lowest rank numbers such that a higher CAFS score indicates a better outcome. The deceased cases will receive the lowest rank numbers followed by the level of decreases in ALSFRS-R scores. Descriptive statistics for this endpoint will be made but are difficult to interpret as mean values depend on the size of the study. In this study, with 300 patients the CAFS scores range from 1 to 300 with a total sum of 28,920 and an overall mean value of 120.5. The difference between treatments will be assessed using an ANCOVA model with the same covariates as the primary efficacy analysis. A rank-ANOVA will be used as a sensitivity analysis. Subsequent component analyses of function and survival will be used to determine which parameter(s) drive the overall effect on the CAFS results. The direction and magnitude of the function and survival components of the CAFS will inform the interpretation of the results.

'Survival', i.e. time to death, tracheostomy or initiation of non-invasive ventilation for more than 20 hours a day for more than 10 consecutive days, over 72 weeks Descriptive statistics (median and 25% and 75% quartiles with 95% confidence intervals) and Kaplan-Meier curves will be provided. The difference between oral FAB122 and placebo will be assessed using restricted mean survival time (RMST) analysis up to week 48 (and week 72), controlling for the stratification variables. In addition, also a Cox regression model and a stratified log-rank test will also be applied as sensitivity analysis, including factors for treatment and stratification variables.

##### Other secondary endpoints

The following exploratory secondary endpoints will also be summarized, as applicable: Continuous endpoints will be summarized by descriptive statistics (mean, median, standard deviation, minimum and maximum), but can also be summarized with frequency count and percentage for appropriated categories. These will be defined in the SAP. Binary or categorical endpoints will be summarized with frequency counts and percentages. Time to event endpoints will be summarized by median values with 95% confidence intervals. The statistical method that will be applied for each endpoint will be detailed in the SAP.

- Change from baseline in ALSFRS-R score after 24 and 72\* weeks;
- The slope of the decrease in ALSFRS-R score over time at 24, 48 and 72\* weeks;

- Change from baseline in ALSFRS-R score on Bulbar function (question 1-3 of the ALSFRS-R) after 24, 48 and 72\* weeks;
- Change from baseline in ALSFRS-R score on Fine motor function (question 4-6 of the ALSFRS-R) after 24, 48 and 72\* weeks;
- Change from baseline in ALSFRS-R score on Gross motor function (question 7-9 of the ALSFRS-R) after 24, 48 and 72\* weeks;
- Change from baseline in ALSFRS-R score on Respiratory function (question 10-12 of the ALSFRS-R) after 24, 48 and 72\* weeks;
- Time to a 3, 6, 9 and 12 points change or death from baseline in ALSFRS-R score over 72\* weeks;
- Proportion of subjects with change from baseline in ALSFRS-R score at 24, 48 and 72\* weeks in categories: categories will include change  $\geq 0$ , change between  $< 0$  and  $\geq -1$ , change between  $< -1$  and  $\geq -2$  etc.;
- Time to change in clinical staging or death (King's staging system and MiToS) over 72\* weeks;
- Overall survival: Proportion of subjects alive (survival rate) after 24, 48 and 72\* weeks;
- Proportion of subjects alive and no tracheostomy, or no initiation of non-invasive ventilation for more than 20 hours a day for more than 10 consecutive days after 24, 48 and 72\* weeks;
- Change from baseline in slow vital capacity (SVC, liters) at 24, 48 and 72\* weeks;
- Change from baseline in the overall mega score for the hand-held dynamometer (HHD) at 24, 48 and 72\* weeks.

#### QoL

- Change from baseline in the total score on the ALS Assessment Questionnaire-40-Item (ALSAQ-40) Form at 24, 48 and 72\* weeks;
- Change from baseline in EuroQoL – 5 Dimensions-5 Levels (EQ-5D-5L) questionnaire score 24, 48 and 72\* weeks.
- Change from baseline in Health related QoL Visual Analogue Scale (VAS) score at 24, 48 and 72\* weeks.

#### Cognition

- Proportion of subjects with a change of  $\geq 8$ ,  $\geq 4$ , and  $\geq 9$  for ALS Specific, ALS Non-Specific, and ECAS (Edinburgh Cognitive and behavioural ALS Screen) total score;
- Change from baseline for ALS specific and ALS non specific, and ECAS total score at 24, 48 and 72\* weeks.
- Time to a mean change of  $\geq 8$ ,  $\geq 4$ , and  $\geq 9$  for ALS Specific, ALS Non-Specific, and ECAS total score.

\*All secondary endpoints at 72 weeks will be analyzed for the subgroup of patients that reach 72 weeks (or IE).

#### 11.3.4.4. Additional analysis

As an additional analysis, the joint assessment of change in functional decline and overall mortality using a joint modelling (i.e. shared-parameter) framework over 72 weeks will be determined. The statistical model will combine ALSFRS-R score and survival, using a linear mixed model and a Cox model as sub models combined into a non-linear mixed model using the SAS procedure PROC NLMIXED.

#### 11.3.5. PK Analysis

Refer to the PAP for full analysis details. Differences between scheduled and actual PK sampling times will be listed for all subjects. All statistical summaries and displays will be based on scheduled sampling times unless there are significant deviations of actual sampling times from scheduled sampling times.

Concentration-time data and PK parameters will be summarized by treatment group with summary statistics at each scheduled time point, where applicable. Summary statistics will include: Number (N), mean, standard deviation (SD), coefficient of variation (%CV), median, minimum (min), maximum (max). In addition, geometric mean and CV% geometric mean will be presented for  $C_{max}$  and  $AUC_{last}$ .

Each subject's exposure to study drug will be summarized using descriptive statistics, as described in detail in the PAP.

#### 11.3.6. Safety Analysis

Safety evaluations will be based on the incidence, severity, and type of AEs and clinically significant changes in the subject's physical examination findings, vital signs, and clinical laboratory results. Safety variables will be tabulated and presented for all subjects in the Safety Population. Data will be summarized by treatment and time. Exposure to study drug and reasons for discontinuation of study drug will be tabulated.

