#### 11.3.6.5. ECG

From the 12-lead ECG data, HR, PR, QRS, QT, and QTcF will be reported for each time-point and summarized using descriptive statistics. Mean (SD) temporal profiles for 12-lead ECG (QT, QTcF) will be presented graphically. The frequency (number) of clinically significant findings may be reported and summarized.

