### 5.5.4 Disposition

To present disposition, a summary of all included, randomised, treated and completed patients will be created. Number/percentage screened will be included as well, if available in the database. Additionally, in the same summary, the number/percentage of patients in the ITT, mITT, PP, PK and SAF will be presented and the frequency/percentage per reason for non-completion will be added. The patient disposition will be presented per treatment group and overall.

Additionally, a listing displaying all disposition information (including reasons for withdrawal and reasons for exclusion from the PP population) on a per patient level will be created. This listing will include exposure time for each patient, calculated from date of first dose until end of treatment, and follow-up time for each patient, calculated from date of first dose until end of study.

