### **5.7.3 Vital Signs**

Vital sign data will present measurements for height, weight, BMI, systolic and diastolic blood pressure, pulse rate, respiratory rate, pulse oximetry and temperature. Vital signs (absolute values and change from baseline) will be summarized (n, mean, SD, median, minimum and maximum) and listed per visit, per treatment group and overall, using protocol visits. Mean (SD) of absolute values for vital signs data (blood pressure, pulse rate and respiratory rate) will also be presented graphically through time.

If applicable, vital sign measurements collected as additional/unscheduled assessments (i.e. apart from those per protocol) will only be listed and will not be used in summary statistics or graphical presentations.

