### **5.7.4 ECG**

From the 12-lead ECG data, HR, PR interval, QRS interval, QT interval, RR interval and QTcF will be reported for each visit and summarized using descriptive statistics. Change from baseline will be calculated as well, using the same summary statistics. Mean (SD) temporal profiles for 12-lead ECG (QT, QTcF) will be presented graphically. Clinically significant findings will only be listed.

If applicable, ECG measurements collected as additional/unscheduled assessments (i.e. apart from those per protocol) will only be listed and will not be used in summary statistics.

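### The SAP lists exposure to study drug per patient instead of tabulating it as protocol 11.3.6 requires, and SAP 5.7.6 does the same for physical-examination abnormalities

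*Protocol*

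**What the plan says.** **Exposure.** Protocol 11.3.6 commits to a table: "Exposure to study drug and reasons for discontinuation of study drug will be tabulated". It also says "Safety variables will be tabulated and presented for all subjects in the Safety Population", with summaries by treatment and time. SAP 5.5.4 places exposure in a patient listing: "This listing will include exposure time for each patient, calculated from date of first dose until end of treatment". SAP 5.8.2 lists dosing information per patient, and its only table is percent compliance in three bands. SAP 10.3 has Disposition (14.1.3) and Compliance (14.1.6) but nothing on time on drug. SAP 10.4 carries treatment exposure as listing 16.2.4.1.

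**Physical examination.** Protocol 11.3.6.1 asks for abnormalities to be both listed and put in a table by arm. SAP 5.7.6 keeps only the listing, although SAP 10.3 has an output numbered 14.3.4.10 with that title.

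**ECG and vital signs.** Protocol 11.3.6 bases the safety evaluation on adverse events and on "clinically significant changes in the subject's physical examination findings, vital signs, and clinical laboratory results"; ECG is not named there. For ECG, protocol 11.3.6.5 says "The frequency (number) of clinically significant findings may be reported and summarized", and SAP 5.7.4 says "Clinically significant findings will only be listed". For vital signs, protocol 11.3.6.6 asks for descriptive statistics by time point and arm, and SAP 5.7.3 supplies them.

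**Declared changes.** SAP section 6 records departures from the protocol down to spelling corrections. It mentions none of the above.

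**The concern.** The adverse-event tables in SAP 5.7.1 give numbers of patients, numbers of events and percentages of patients. How those compare between arms depends on how long each arm was on drug and under observation, and four features of the design make that uncertain:

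- A TEAE is any event from first dose onward (protocol 9.1.1, SAP 5.7.1), with no cut-off after the last dose, so events off drug count.
- Patients may stop drug and continue visits (protocol 6.5).
- The first 100 patients are followed to week 72 and the rest to week 48 (protocol section 4 and Table 1, note 1), so one percentage mixes two observation periods.
- Protocol 11.4 expects more stops on FAB122, both for adverse events and for lack of efficacy.

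If more of the FAB122 period is off drug, a drug-related excess is diluted in the crude percentages. Without a by-arm exposure table, a reader of the report's tables cannot see whether that dilution is trivial. If the table is built only after unblinding, its denominators will be chosen with the results in view.

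**Working it through.** The plan states no figure on this point, so there is none to reproduce. The check is a comparison of texts, followed by an illustration of size.

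**1. Is the promised table anywhere in the SAP?** Exposure time is derived for each patient, but only for listings. Section 10.3 names no exposure table.

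**2. Can the compliance table stand in for it?** No. SAP 5.8.2 divides sachets taken by the days between that patient's first and last dose. A patient who stops at week 6 having taken every sachet scores 42/42 = 100%, the same as one who takes every sachet to week 72. Early stopping is invisible in that measure.

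**3. Does the PK plan supply it?** Protocol 11.3.5 says each subject's exposure will be summarised as set out in the PK analysis plan. That plan is not among the documents. The sentence sits in the PK section, and the PK population is limited to subjects with evaluable PK data, with sampling in about 90 subjects (protocol 6.7 and 11.3.1). It does not clearly deliver a table for the whole safety set.

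**4. How large might the imbalance be?**

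Inputs from the protocol: 100 patients planned to 72 weeks and 200 to 48 weeks; 2:1 allocation; expected stops for adverse events of 7% on FAB122 and 3% on control, and for lack of efficacy of 10% and 5% (section 11.4). Treating the two reasons as separate patients gives 7 + 10 = 17% and 3 + 5 = 8%.

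Planned exposure: 100 × 72 + 200 × 48 = 16,800 patient-weeks, or 16,800/300 = 56 weeks per patient. At 52.18 weeks per year this is about 322 patient-years. With exact 2:1 allocation in both follow-up groups, that is about 215 on FAB122 and 107 on placebo.

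Assumption: a patient who stops loses on average a share *f* of planned exposure. The documents do not give *f*, so 0.25 to 0.75 is shown. The share of planned drug time retained is 1 − (stop rate × *f*).

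| *f* | FAB122 | Placebo | Ratio | Mean weeks on drug | Patient-years |
|---|---|---|---|---|---|
| 0.25 | 1 − 0.17 × 0.25 = 0.9575 | 1 − 0.08 × 0.25 = 0.980 | 0.977 | 53.6 v 54.9 | 206 v 105 |
| 0.50 | 0.915 | 0.960 | 0.953 | 51.2 v 53.8 | 196 v 103 |
| 0.75 | 0.8725 | 0.940 | 0.928 | 48.9 v 52.6 | 187 v 101 |

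Mean drug time is about 2-7% lower on FAB122.

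**5. Physical examination.** Protocol 11.3.6.1 requires a list and a by-arm table; SAP 5.7.6 requires a list only. Output 14.3.4.10 may be meant as the table, but the SAP text does not say so. The two sections need to be reconciled.

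**The case against.** The strongest reply is that little is lost. Exposure and follow-up time are derived for every patient, and the listings carry treatment as a key variable, so by-arm rates can be worked out at any time. Reasons for non-completion are tabulated by arm in the disposition table, and TEAEs leading to premature discontinuation have their own table, so the second half of the quoted protocol sentence is largely met. A 2-7% difference in drug time would hardly move a comparison of percentages, and no hypothesis test depends on it. The protocol never asked for exposure-adjusted rates. All of this is fair, and it limits the weight of the point. It does not supply the table that the protocol commits to, and the 2-7% is a planning illustration; the actual difference is what the table would show.

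A reader might infer something stronger: that the SAP also withdrew promised by-arm counts of clinically significant ECG and vital-sign changes. The documents do not support that. The ECG count was optional in protocol 11.3.6.5, so listing the findings is within the protocol. The general sentence in 11.3.6 says what the safety evaluation rests on, while the specific vital-signs subsection asks only for descriptive statistics, which the SAP gives by visit and arm, minimum and maximum included. Protocol 9.1.1 also makes an abnormal laboratory or diagnostic result an adverse event when the investigator considers it clinically significant, so such ECG findings should reach the by-arm TEAE tables. The phase I trials summarised in protocol 2.2 report no clinically significant 12-lead ECG values.

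**Conclusion.** The point holds for exposure and for physical examination. The protocol requires both to be tabulated, the SAP text provides listings, and SAP section 6 does not declare the difference. The consequence is that the adverse-event percentages have no pre-specified by-arm drug-time denominator, in a design where time on drug is expected to differ between arms.

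The expected size is modest, at about 2-7% less drug time on FAB122. That rests on the protocol's expected stop rates, on adding the two stop reasons, on exact 2:1 allocation in both follow-up groups, on an assumed loss of 25-75% of planned exposure per stopping patient, and on ignoring deaths and other reasons for stopping. Unequal follow-up alone should not unbalance randomised arms, but it makes a single percentage harder to interpret.

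Two stronger readings should be set aside. It is not the case that rates and counts could never be obtained; they are simply not pre-specified. Nor is the lack of by-arm ECG or vital-sign counts a broken protocol commitment. Adding them would be an improvement.

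**What to change.** 1. **Exposure (SAP 5.8.2 and 10.3).** Add a by-arm table for the safety set with weeks on drug, weeks followed and total patient-years on drug. Beside the percentages for TEAEs, SAEs and AESIs, give exposure-adjusted rates. The table meets the protocol's commitment; the rates go beyond it and are its natural use.
2. **Physical examination (SAP 5.7.6).** State that abnormalities are tabulated by arm as well as listed, and tie this to output 14.3.4.10. If listing only is intended, say so in SAP section 6.
3. **Optional.** In SAP 5.7.4, replace listing-only with by-arm counts of patients with any clinically significant ECG finding. Add by-arm counts of marked QTcF and vital-sign changes, using limits fixed before unblinding.

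The cost is some SAP wording and a few extra tables from data already collected. There is no change to visits, sample size or any hypothesis test.
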